8.3 ELECTRONIC CASE REPORT FORMS

All study data will be entered into an Electronic Case Report Form (eCRF). The investigator is responsible for ensuring the accuracy of all data entered on the eCRF. Each eCRF entry must be supported by source documentation in the subject's medical records.

8.4 MEASURES AND METHODS OF ASSESSMENT

The following assessments will be utilized throughout the study in accordance with the assessment schedules described in sections 9 and 10.

8.4.1 Demographic information

Age, gender, race, BMI, osteoarthritis diagnosis and treatment history, comorbidities, and concomitant medications will be collected for demographic analysis.

8.4.2 Index Knee

The "index" knee is defined as the knee that is being studied and to which the eligibility criteria are applied. This is the knee that will be treated with either CRFA or HA injection. Subjects may have moderate osteoarthritis in the contralateral limb and still be included in the clinical trial; however, only one knee may meet eligibility and be entered into the study.

8.4.3 Radiographic Evaluation

All subjects are required to have radiographic confirmation of arthritis (x-ray/MRI/CT) of OA grade of 2 (mild), 3 (moderate) or 4 (severe) noted within 6 months prior to study enrollment. OA grade will be based on the classification system of Kellgren-Lawrence²³ diagnosed by standard x-rays. Radiographic evaluations will also be assessed at each subject's Visit 6 (12 Month Visit) and at 24 months as appropriate.

8.4.4 Subject Reported Clinical Symptoms of Chronic Knee Pain

All subjects are required to complete a Numeric Rating Scale²⁴ (NRS) for pain at multiple points during the clinical study. Subjects will be asked to rate their usual pain, worst pain, least pain, and current pain in each knee at each time point. An NRS of \geq 6 (usual daily pain) for their index knee is required for entrance in the study. An accurate assessment of NRS is critical at all points in the study, especially at the 6-month visit, as this will be used as the primary endpoint of the study.

8.4.5 Combined Investigator/Subject Reported Outcomes

The WOMAC is a disease-specific validated outcomes instrument that is routinely used to evaluate the overall condition of subjects with osteoarthritis of the knee²⁵. This instrument assesses pain, stiffness and physical function subscales and requires inputs from both the subject and the investigator.

For study inclusion, WOMAC Knee Score group at baseline of Score of 2 or 3 (0 to 4 scale) on WOMAC question A1 (pain while walking on flat surface) and a mean score of 1.5 to 3.5 on all five questions of the WOMAC subscale A (pain) are required.

8.4.6 Intraoperative Radiographic Assessment

An antero-posterior (AP) and lateral fluoroscopic views of the treated knee will be obtained intraoperatively to confirm placement of the RF probes. The images must be captured on archive media and maintained as described in section 6.6.4.

8.4.7 Post-Treatment Care

Unless there is an adverse event requiring further medical intervention, subjects will be discharged home from the treatment facility on the day of the procedure with strict instructions for a caregiver or other individual to drive them home. Subjects will be encouraged to refrain from strenuous activity for 48 hours following both procedures. It is anticipated that subjects will feel some pain and discomfort at the site of the procedure for up to 1-2 weeks following the procedure. Subjects will be instructed to use common conservative therapy such as ice packs at the procedure site and may be prescribed analgesic medication to decrease their discomfort, if needed. Subjects will be instructed to return to ambulation based upon their own pain tolerance and using any modalities such as a cane that was employed prior to the RF procedure.

8.4.8 Subject-Reported Quality of Life Outcome Measures

The EQ-5D-5L scale ²⁶, a validated instrument for subject quality of life and overall health status, will be obtained at all visits. The EQ-5D-5L allows assessments of impact on healthcare systems to be undertaken.

The Global Perceived Effect (GPE) scale²⁷, a validated instrument for subject quality of life outcomes, will be used for this study. The GPE has been validated to measure health transitions in subjects with musculoskeletal disorders such as osteoarthritis. The GPE will be obtained at all follow up visits.

9 SCHEDULE OF ASSESSMENTS

Table 1: Schedule of Assessments

										Extensi	on Study
	V1	V2	V3	V4	V5	V5A ²	V5B ²	V5C ²	V6	V7	V8
	Screen/ Rand.	Index Procedure / Treatment (DAY = 0)	1 Month	3 Months	6 Months	Cross- Over Tx (DAY = 0)	Post Cross-	3 Months Post Cross- Over	12 Months (Tx Group) or 6 Months (Crossover)	18 Months (Tx Group)	24 Months (Tx Group)
	Complete Within 60 Days of ICF	Within 30 Days of Randomizat ion	30 +/- 7 Days	90 +/- 14 Days	180 +/- 14 Days from Treatme nt	Within +30 Days	30 +/- 7 Days from V5A	90 +/- 14 Days from V5A	360 +/- 14 Days or 180 +/- 14 Days from V2/5A	540 +/- 14 Days from V2	720+/- 14 Days from V2
Informed Consent	X					X				X	
Inclusion/Exclusion	X	X ¹				X ¹					
Pregnancy Test (if applicable)	X	X				X					
Relevant Medical History	X										
Radiographic Exam	X ⁵								Х		X
Physical Exam	X ³				Х				Х	Х	X
Knee Exam	X				X				X	Х	X
Diagnostic Block Procedure	X										
Beck's Depression Index	X										
Numeric Rating Scale	X		Х	X	X	X	X	Х	X	X	X
WOMAC	X		Х	X	X	X	X	Х	X	X	X
EQ-5d	X		X	X	Х	Х	X	Х	X	X	X
Healthcare Utlization	X	X	Х	X	Х	X	X	Х	X	Х	X
Global Perceived Effect Score			X	X	Х	X	X	X	X	Х	Х
Randomization	X										
Coolief (CRFA) Applications		X				X ²					
Viscosupplementation (HA) Knee Injection		X									
Adverse Event Assessment⁴	Х	X	X	X	X	X	X	X	Х	Х	X
Concomitant Medication Assessment	X	X	Х	X	Х	X	X	Х	х	Х	Х
Patient Stipend (if applicable)	X	X	X	X	X	X	X	X	X	X	X

Verify continued eligibility

10 PROCEDURES BY VISIT

10.1 VISIT 1- Screening / Randomization

Perform the following assessments:

- (1) Subject Selection / Informed Consent.
- (2) Follow institutional standard protocol for confirming pregnancy status prior to treatment.
- (3) Obtain demographic information and medical history.
- (4) Assess subject radiographs for eligibility.
- (5) Perform Physical Exam (including BMI and vital signs).
- (6) Knee exam
- (7) Obtain baseline Beck's Depression Index (subject completed questionnaire).

Crossover Subjects only. Visits 5B, 5C and 6 based off Visit 5A date for crossover subjects.

³ Includes BMI and vitals during exam at all visits.

⁴ Includes Concurrent Knee Procedures

⁵ Acceptable within 6 months of ICF

- (8) Perform Numeric Rating Scale assessment for pain (subject completed questionnaire).
- (9) Obtain a baseline WOMAC Score (subject completed questionnaire).
- (10) Obtain a baseline EQ-5D-5L Score (subject completed questionnaire).
- (11) Obtain Healthcare Utilization Form
- (12) Assess concomitant medications.
- (13) Verify that diagnostic block procedure was performed and confirm responder status.
- (14) Verify subject eligibility and randomize subject.
- (15) Perform adverse event assessment (if screening visit occurs over more than one day)
- (16) Assess concomitant medications.
- (17) Schedule Treatment visit

The screening procedures/visit can occur on more than one day, but must be concluded (patient should be randomized) within 60 days of signing informed consent.

10.2 Visit 2 – Index Treatment (Day 0)

It is permissible that Visit 2 can occur on the same day as Visit 1/Randomization date, but it should occur within 30 days from the date of randomization.

Perform the following assessments:

- (1) Verify that subject continues to meet all eligibility criteria.
- (2) Follow institutional standard protocol for confirming pregnancy status prior to treatment (if applicable and >30 days since previous one)
- (3) Obtain Healthcare Utilization Form
- (4) Perform CRFA or HA injection procedure per section 6.6.4.
- (5) Perform adverse event assessment.
- (6) Assess for changes to concomitant medications.
- (7) Provide subject with perioperative care and at-home care instructions
- (8) Schedule next clinic visit

It is recommended (but not required) that the first several CRFA procedures at each site should be proctored by a Avanos Medical clinical specialist to ensure procedural consistency between sites.

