6.6.3 Treatment Assignment

At visit 1, all subjects who meet the eligibility criteria will be randomly assigned to one of two groups: (A) CRFA or (B) HA injection. Randomly generated treatment assignments (1:1 randomization) have been prepared by the study statistician using a computerized randomization program, and will be loaded into the electronic data management system being utilized in the study. Upon confirmation that a subject is eligible for randomization, sites will log into the system to randomize the subject. Specific instructions will be provided. The monitor will confirm that the randomization process is being appropriately followed and documentation is being maintained as appropriate. Any deviation from the randomization process must be immediately reported to the sponsor and IRB as appropriate and documented appropriately.

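### Pain eligibility is to be re-verified after assignment with no pain score scheduled, and a subject left untreated as a result drops out of the primary analysis set

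*Combined protocol and SAP*

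**What the plan says.** **Order of events.** Section 6.6.3 places assignment before the treatment visit: "At visit 1, all subjects who meet the eligibility criteria will be randomly assigned to one of two groups". Screening may take more than one day but "must be concluded (patient should be randomized) within 60 days of signing informed consent" (10.1). For Visit 2, section 10.2 says "it should occur within 30 days from the date of randomization"; the same day is allowed.

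**Pre-treatment scores.** Table 1 and section 10.1 schedule NRS, WOMAC and EQ-5D-5L once before treatment, at Visit 1, with no rule on which screening day. The NRS is both an entry criterion (7.1 item 6; 8.4.4) and the reference for the 50% reduction (12.6.1, whose HA definition names Screening).

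**Visit 2.** Item 1 of section 10.2 is to "Verify that subject continues to meet all eligibility criteria". Neither the rest of that list nor the Visit 2 column of Table 1 contains NRS, WOMAC or EQ-5D-5L. Section 8.4.8 nevertheless says that the EQ-5D-5L "will be obtained at all visits".

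**Analysis set.** Section 12.2.2 limits the Full Analysis Set, used for the primary analysis, to randomized subjects who were treated and have at least one effectiveness observation.

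**Blinding.** Section 6.3 lists measures against bias; blinding of subject or site is not among them. The two procedures in 6.6.4 are plainly different.

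**The concern.** Item 1 cannot be carried out as written for the pain criteria. The site must reuse the Visit 1 score, pass over those criteria, or judge current pain informally. The last course is the one that matters: the judgement would come after assignment, with the arm apparently known, and a subject not treated because of it would leave the primary analysis set. If such decisions differ between arms, the comparison is no longer between the groups that were randomized.

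A second, smaller matter is the age of the baseline. Subjects are selected on one reading of at least 6, and that reading is then the denominator of the response definition. Some will read lower later without any treatment effect. This raises response rates, including the 18- and 24-month CRFA rates, which have no concurrent control.

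The plan elsewhere allows for long gaps. Section 10.2 item 2 repeats the pregnancy check when the last is more than 30 days old, and the crossover visit (10.6) collects NRS, WOMAC and EQ-5D-5L at Visit 5A, or the same day as part of Visit 5. The randomized treatment visit has no counterpart for the pain score.

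**Working it through.** **1. The plan's own sample size.** Inputs from 12.1: 62% against 40%, margin 5 points, two-sided 5%, 90% power, 1:1.

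n per arm = (1.960 + 1.282)² × (0.40×0.60 + 0.62×0.38) / (0.22 + 0.05)² = 10.51 × 0.4756 / 0.0729 = 68.6, so 69 per arm and 138 in total, against 134 stated. Power at 67 per arm is 89.3%. With 20% attrition, 168 × 0.8 = 134.4. The plan's figure is reproduced closely, and nothing below changes it.

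**2. Age of the baseline at treatment.** Maximum: 60 days (consent to randomization) + 30 days (randomization to treatment) = 90 days. Minimum: 0 days. With the oldest baseline, the 6-month visit (180 ± 14 days) falls 90 + 166 = 256 to 90 + 194 = 284 days after it.

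**3. The re-check against the schedule.**

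| Criterion to be re-verified | Source | Scheduled at Visit 2? |
|---|---|---|
| NRS at least 6 | 7.1 item 6 | No |
| WOMAC question 1 and pain-subscale mean | 7.1 item 9 | No |

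The WOMAC entry limits also differ between sections: 7.1 gives lower limits only, while 8.4.5 gives closed ranges (2 or 3 on the first question, mean 1.5 to 3.5). These must be reconciled before either can be applied.

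**4. How many subjects might read below 6 on a repeat.** The documents give no retest data, so this is an illustration. Assumptions: NRS before selection has mean 5.5 to 6.5 and SD 1.8 to 2.0, retest correlation is 0.6 to 0.9, and subjects are selected at 6 or more. The selected means are 7.1 to 7.4, near the 7.3 ± 1.2 of the earlier CRFA trial (4.4). About 9% to 30% would read below 6 on an untreated repeat: 0.09 × 168 = 15 to 0.30 × 168 = 50 subjects. About 0% to 6% would show a fall of 50% or more. The model has no time component, so these figures do not measure the effect of a 90-day gap.

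**5. Effect on the between-arm difference.** Let a share r of non-responders in each arm count as responders through fluctuation. Each rate p becomes p + (1 − p)r, and the difference becomes 0.22(1 − r).

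| r | HA | CRFA | Difference | NI power, 67 per arm | Superiority power |
|---|---|---|---|---|---|
| 0 | 40.0% | 62.0% | 22.0 | 89% | 74% |
| 5% | 43.0% | 63.9% | 20.9 | 87% | 70% |
| 10% | 46.0% | 65.8% | 19.8 | 84% | 65% |

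The difference shrinks; it does not move in favour of CRFA. The last row lies beyond the range found in step 4.

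**6. Level against difference.** In a similar model (mean 6.0, SD 1.8, correlation 0.65), response with 30% true relief is 25.1% on the screening baseline and 21.3% on a second reading of at least 6. With 40% relief it is 44.4% and 40.9%. Each level moves by 3.5 to 3.8 points. The contrast between the two relief levels is 44.4 − 25.1 = 19.3 on the first baseline and 40.9 − 21.3 = 19.6 on the second, a change of 0.3.

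**The case against.** **Baseline drift does not threaten the comparison.** A reader might infer that fluctuation adds 2.4 to 3.8 points of response, the range over the assumed means and correlations, and so uses up most of the 5-point margin. The documents do not support this. The margin applies to the difference between arms (12.6.1), whereas the 2.4 to 3.8 points are a rise in level expected in both. The figure also does not come from an old baseline: among subjects who pass both readings, response is the same whichever reading is the denominator, so the reduction comes from requiring a second pass. It depends, too, on assuming 30% to 40% relief, just below the cutoff. The earlier trial's CRFA means (7.3 to 2.5 in 4.4, or 4.8/7.3 = 66% relief) bring the shift below 1 point. This objection stands in full.

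**The decision would leave a record.** A reader might infer that subjects could be dropped at Visit 2 without trace. Section 10.5 requires discussion with the sponsor before an investigator withdraws a subject, except in emergent safety cases, and lists NRS and WOMAC among the exit procedures where possible. Section 12.1.1 summarizes reasons for early termination, and 12.1.2 requires waivers in writing. This stands as far as it goes. But an exit score is taken once exit is being arranged, is not mandatory, and does not return the subject to the Full Analysis Set.

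**Nothing shows that sites will exclude for pain.** True. Entry also rests on usual pain, with pain lasting more than 6 months and stable analgesics, which argues against large swings. Ninety days stacks two maxima. What remains is a rule that permits the problem, not evidence that it occurs.

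**Conclusion.** The point holds as an inexpensive improvement, not as a threat to the primary conclusion. Section 10.2 item 1 asks for a post-assignment check of pain criteria that the schedule gives no means to make, and 12.2.2 removes untreated subjects from the primary analysis. Together they open a route to arm-dependent exclusion. Its size cannot be derived from the documents. The 15 to 50 subjects in step 4 show only how many might read below 6 on a repeat, under assumed retest correlations.

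The baseline may be up to 90 days old at treatment. Drift in it is equal between arms in expectation, raises both response rates and, at r = 5%, would reduce the difference by about 1 point. That figure rests on assumption. Drift does not by itself favour one arm and should not be set against the 5-point margin.

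That the arm is known at Visit 2 is inferred from the procedures and from the absence of any described blinding; the plan does not state it.

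**What to change.** 1. In 10.1 and Table 1, take NRS (usual pain), WOMAC and EQ-5D-5L on the day of randomization, before any same-day block and before the assignment is released. Name these values as the baseline for every change endpoint and as the values for inclusion items 6 and 9. Reconcile the WOMAC limits in 7.1 and 8.4.5 at the same time.
2. Reconcile 10.2 item 1 with Table 1 so that pain-score eligibility is settled before assignment and not re-judged afterwards.
3. Report randomized-but-untreated subjects by arm with reasons, and add a sensitivity analysis of the primary endpoint that keeps them.
4. Reconcile the EQ-5D-5L wording in 8.4.8 with Table 1.

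**Cost.** Three short questionnaires are repeated when screening spans several days, and a few more subjects fail screening. The planned 168 does not change.

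**What remains.** Up to 30 days may still pass between baseline and treatment, so the 6-month visit can fall 30 + 194 = 224 days after baseline. Subjects are still selected on the reading used as denominator; where all screening is done on one day, the change makes no difference to that.

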10.3 VISIT 3-6 – FOLLOW-UP ASSESSMENTS

Visit 3/1 Month Visit should occur at post-operative day 30 ± 7 days. Visit 4/3 Month Visit should occur at post-operative day 90 ± 14 days. Visit 5/6 Month Visit should occur at post-operative day 180 ± 14 days. Visit 6 should occur at post-operative day 360 ± 14 days.

Perform the following assessments:

- (1) Subjects will return at months 1, 3, 6 and 12 after the procedure within the allowable follow-up intervals described above.
- (2) Obtain a Numeric Rating Scale for pain (subject completed questionnaire).
- (3) Obtain WOMAC Score (subject completed questionnaire).
- (4) Obtain an EQ-5D-5L Assessment (subject completed questionnaire).
- (5) Obtain a Global Perceived Effect Score (subject completed questionnaire).
- (6) Obtain Healthcare Utilization Form
- (7) Perform Physical Exam including BMI and vital signs (Visits 5 and 6 only).
- (8) Perform Knee Exam (Visits 5 and 6 only).
- (9) Perform adverse event assessment.
- (10) Assess concomitant medications.
- (11) Schedule next clinic visit.
- (12) Collect and assess Radiographs (Visit 6 only).

10.4 VISIT 7-8 – LONG TERM FOLLOW-UP ASSESSMENTS

These visits are only available to those subjects who originally received CRFA at Visit 2 and who signed the informed consent to continue participation in the study. Visit 7/18 Month Visit should occur at post-operative day 540 ± 14 days and Visit 8/24 Month Visit should occur at post-operative day 720 ± 14 days.

Perform the following assessments:

- (1) Obtain Informed consent (only at Visit 7).
- (2) Obtain a Numeric Rating Scale for pain (subject completed questionnaire).
- (3) Obtain WOMAC Score (subject completed questionnaire).
- (4) Obtain an EQ-5D-5L Assessment (subject completed questionnaire).
- (5) Obtain a Global Perceived Effect Score (subject completed questionnaire).
- (6) Obtain Healthcare Utilization Form.
- (7) Perform Physical Exam including BMI and vital signs.
- (8) Perform Knee Exam.
- (9) Perform adverse event assessment.
- (10) Assess concomitant medications.
- (11) Schedule next clinic visit (only at Visit 7).
- (12) Collect and assess Radiographs (only at Visit 8).

10.5 DISCONTINUATION / EARLY TERMINATION (ET)

Subjects may withdraw from the study at any time for any reason. Early terminations can occur under the following circumstances:

- 1. Subject withdraws consent.
- 2. Subject receives an additional procedure on their index knee.
- 3. Investigator withdraws the subject for any reason following discussion with the sponsor.
- 4. Investigator withdraws the subject immediately for emergent safety issues and reverts to institutional standards-of-care.

If it becomes necessary to exit the subject from the study early, the following exit procedures should be conducted if at all possible:

- (1) Obtain a Numeric Rating Scale for pain (subject completed questionnaire).
- (2) Obtain WOMAC Score (subject completed questionnaire).
- (3) Obtain an EQ-5D-5L Assessment (subject completed questionnaire).
- (4) Obtain a Global Perceived Effect Score (subject completed questionnaire).
- (5) Obtain Healthcare Utilization Form
- (6) Collect and assess Radiographs
- (7) Perform Physical Exam including BMI and vital signs
- (8) Perform Knee Exam
- (9) Perform adverse event assessment.
- (10) Assess concomitant medications.

The study may be terminated by the sponsor at any time for any reason. If a subject is withdrawn or the study is terminated, investigators will revert to institutional standards-of-care.

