6.3 MEASURES TO MINIMIZE/AVOID BIAS

All subjects presenting to the study centers who report knee pain will be evaluated for eligibility for study participation. Routine evaluations of all site screening logs will be conducted to assure that no subjects are excluded based on investigator bias. Further, the primary endpoint measurements in this study are primarily subject generated and are not based on the opinion of the investigator, thus minimizing the potential for bias related to the outcome of the procedure.

Independent monitoring, Data Management and Statistics will also be utilized to ensure accuracy of the data collected.

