10.6 Crossover visit (visit 5a)

Only subjects initially randomized to the control group (HA injection) who remain in **significant** pain at Visit 5 are eligible to receive crossover. Significant pain is defined as pain substantial enough to warrant receipt of a minimally invasive procedure (i.e., CRFA) per the investigators and subject assessment. Subjects do not need to formally requalify for the study to receive crossover per the inclusion/exclusion criteria; however, *confirmation and documentation is needed that subjects remain a medically appropriate candidate* for the CRFA procedure in order to be eligible.

Prior to receiving the Crossover procedure, the subject should be reminded of the risks of the CRFA procedure as described in section 4.6 and should sign the Crossover section of the informed consent document as noted in Section 8.2.

If the subject is still receiving relief from the HA injection at the time of this visit and/or is not medically appropriate for the CRFA procedure or elects not to Crossover, the subject should not receive crossover treatment and should continue to complete Visit 6.

It is anticipated that the Crossover procedure will occur on a different day than the 6 Month visit (Visit 5); however, it is allowable to perform the procedure on the same day if the Visit 5 items are completed first. Otherwise, the crossover treatment should occur within 30 days of Visit 5. If Visit 5A occurs on the same day as Visit 5, overlapping assessments noted below that were completed as part of Visit 5 do not need to be re-done (i.e., NRS, WOMAC, Healthcare Utilization, etc.).

If a subject choses crossover, the timing of their follow up visits (5B, 5C and 6) will now be based off their Visit 5A treatment date. Visit 5B/1 Month Visit should occur at post-operative day 30 ± 7 days. Visit 5C/3 Month Visit should occur at post-operative day 90 ± 14 days and the 6 Month Visit/Visit 6 should occur at post-operative day 180 ± 14 days.

At the Crossover Visit, the following assessments must be performed.

- (1) Verify Crossover consent was obtained
- (2) Verify and document that the subject remains medically appropriate for the procedure.
- (3) Obtain a Numeric Rating Scale for pain (subject completed questionnaire).
- (4) Obtain WOMAC Score (subject completed questionnaire).
- (5) Obtain an EQ-5D-5L Assessment (subject completed questionnaire).
- (6) Obtain a Global Perceived Effect Score (subject completed questionnaire).

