12.1 DETERMINATION OF SAMPLE SIZE

A non-inferiority approach on response rate was used to estimate the sample size for this study, with "response" defined as \geq 50% reduction in pain on the NRS scale from baseline. The upper bound of a 2-sided 95% CI will be calculated for the rate difference between treatments (Standard minus Test). If the upper bound is less than (δ), then "non-inferiority" is achieved for the test treatment relative to standard treatment, as described in the table below:

Success Rate of CRFA (based on 50% Pain Score Reduction in VAS)	Success Rate of Standard (Based on 30% Pain Score Reduction in VAS)	Non-Inferiority Margin (δ)	Sample Size 5% Level of Significance (2-sided) 90% Statistical Power
62%*	40%**	5%	134

^{* - 14} Davis, et al, RAPM 2017, In Press /FDA clearance K163461

Assuming an attrition rate of 20%, 168 subjects enrolled into the study will yield 134 completers.

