12.2.2 Full-Analysis Set

All randomized subjects will be analyzed following the principle of intention-to-treat (ITT) provided they received CRFA or HA injection treatment and had at least one effectiveness observation.

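### After an investigator's discretionary withdrawal (Section 10.5, item 3) the plan stops seeking the month-6 NRS, so missing primary outcomes can depend on arm and earlier pain

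*Combined protocol and SAP*

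**What the plan says.** Section 10.5 gives four routes to early termination. Withdrawal of consent, a further procedure on the index knee, and emergent safety issues each have their own item. Item 3 is the remaining route: "Investigator withdraws the subject for any reason following discussion with the sponsor". No criteria are attached to it.

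For any early exit, "the following exit procedures should be conducted if at all possible", and the list includes the NRS. The section then closes the subject's participation: "If a subject is withdrawn or the study is terminated, investigators will revert to institutional standards-of-care". It requires no later visit.

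The bias controls in Section 6.3 concern entry and scoring. On entry: "Routine evaluations of all site screening logs will be conducted to assure that no subjects are excluded based on investigator bias". On scoring: "the primary endpoint measurements in this study are primarily subject generated and are not based on the opinion of the investigator". No masking of subject, investigator or sponsor is described, and the two treatments are a fluoroscopically guided ablation and a knee injection.

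On the analysis side, Section 12.2.2 keeps randomized subjects "provided they received CRFA or HA injection treatment and had at least one effectiveness observation". Section 12.8 makes LOCF optional for the primary outcome, promises a sensitivity analysis of the imputation without saying what it is, and imputes nothing for secondary outcomes. Section 12.1.1 will summarize the reasons for early terminations.

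**The concern.** The primary endpoint is response on the NRS at month 6. Each randomized treatment is a single procedure that has already been given when item 3 can apply, so a decision to withdraw the subject is no reason in itself to stop asking about pain. As written, it does stop it. The decision is open-ended and is made by an investigator who, with no masking described, will know the arm and may know how the knee is doing.

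Whether a subject has a month-6 value can then be related both to arm and to earlier pain. What stands in for month 6 depends on when the exit happened and on whether the optional LOCF rule is used. An early response can be frozen, or a subject can have no primary outcome at all. Comparisons of the 12-month NRS and of WOMAC lose these subjects from the time of exit, because those outcomes are not imputed.

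**Working it through.** **Inputs.** From Section 12.1: response 62% (CRFA) and 40% (HA), margin 5 points, 5% two-sided, 90% power, 134 completers. Also from there: "Assuming an attrition rate of 20%, 168 subjects enrolled into the study will yield 134 completers". Allocation is 1:1 (Section 6.1), so 67 completers per arm. The decision rule is the Wald 95% upper bound of HA minus CRFA against 0.05 (Section 12.6.1).

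**The plan's own figure.** Per-arm n = [0.40×0.60 + 0.62×0.38] × (1.960 + 1.282)² / (0.22 + 0.05)² = 0.4756 × 10.51 / 0.0729 = 68.6. This rounds up to 69 per arm, or 138 in all, against 134 stated. Power at 67 per arm is Φ(0.27/√(0.4756/67) − 1.960) = Φ(1.245) = 89.3%. The plan's figure is reproduced closely, and 134/0.80 = 167.5 gives the 168 enrolled.

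**What happens to a subject withdrawn under item 3 before month 6.**

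| Situation | Primary outcome under the plan |
|---|---|
| LOCF used, last NRS shows non-response | Counted as non-responder |
| LOCF used, last NRS shows response | Counted as responder, whatever month 6 would have shown |
| LOCF not used | Missing at month 6 |
| No effectiveness observation | Outside the Full Analysis Set |

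**Illustration of size.** Assume that k = 4 CRFA subjects who would be non-responders at month 6 leave under item 3. The value of k is an assumption; total planned attrition is 0.20 × 168 = 33.6 subjects. Let X and Y be the CRFA and HA responder counts, both binomial with n = 67. Sum the exact probabilities of all (X, Y) for which p_C − p_T + 1.96 × √[p_T(1−p_T)/n_T + p_C(1−p_C)/n_C] falls below the limit.

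- Dropped: p_T = X/63, n_T = 63.
- Carried forward as responders: p_T = (X+4)/67, n_T = 67.
- HA unchanged: p_C = Y/67, n_C = 67.

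| Per arm | Error | k = 0 | 4 dropped | 4 carried as responders |
|---|---|---|---|---|
| 67 | False non-inferiority (true 35% vs 40%, limit 0.05) | 2.7% | 4.6% | 11.1% |
| 67 | False superiority (true 40% vs 40%, limit 0) | 2.7% | 4.7% | 10.1% |
| 84 | False non-inferiority | 2.6% | 4.4% | 9.0% |

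The last row uses the same formula with all 168 subjects retained. The exits are placed in one arm and one direction to show sensitivity. Exits the other way would bias against CRFA.

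**The case against.** The strongest reply is that withdrawal does not remove a subject from the primary analysis. That is right. A reader might infer post-randomization exclusion, and the documents do not support it: the Full Analysis Set keeps anyone treated with one effectiveness observation, an exit NRS is requested, and LOCF is available. If the exit score shows non-response and LOCF is applied, the subject stays in the denominator as a non-responder and the inflation from dropping subjects does not arise.

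Three other inferences also go too far.

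- **That investigator and sponsor act on known scores.** No section says that either sees a subject's NRS when withdrawal is discussed, and the NRS is completed by the subject. At Visit 5 the investigator does judge whether an HA subject has "pain substantial enough to warrant receipt of a minimally invasive procedure (i.e., CRFA) per the investigators and subject assessment", so awareness of pain status is plausible, but it remains an inference. No misuse is shown.
- **That no planned analysis could reveal the problem.** Reasons for exit are summarized, and some sensitivity analysis of the imputation is promised.
- **That four exits equal the margin.** One subject is 1/67 = 1.5 points only if responder status flips. Dropping four non-responders from 67 moves a 40% rate to 26.8/63 = 42.5%, a shift of 2.5 points. The test also rests on a confidence bound: at the planned 62% vs 40% the upper bound is −0.22 + 1.96 × √(0.4756/67) = −5.5 points, well inside the margin.

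It can also be said that optional LOCF affects every kind of exit. That is true, but item 3 is an exit that the investigator initiates while the subject may still be willing to give a score, so the loss is avoidable. The stand-alone SAP announced in Section 12 could fix the imputation rule, but it cannot recover a score that was never requested.

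**Conclusion.** The point holds in this form: in a trial with no masking described, item 3 permits withdrawal without criteria, and the plan then does not seek the primary endpoint at its time point. Missing month-6 data can depend on arm and earlier pain, and what replaces them is an optional rule.

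The size cannot be known from the documents, because the number of item 3 exits is not given or predicted. With four such exits, all CRFA month-6 non-responders, and 67 per arm, false non-inferiority goes from 2.7% to 4.6% if they are dropped and to 11.1% if an early response is carried forward. So LOCF can protect or harm, depending on the last score. These figures assume true rates at the margin and exits all in one direction. If response is near the planned 62% vs 40%, a handful of exits would be unlikely to change the non-inferiority conclusion. This is a should-fix matter of design, cheap to close, and not evidence that the result would be wrong.

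**What to change.** Amend Section 10.5, with a matching line in Section 12.8 and the SAP:

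- An investigator's decision under item 3, and under item 4 where feasible, does not end outcome collection.
- Each such treated subject who has not withdrawn consent is asked for the NRS within day 180 ± 14, by telephone if a visit is not possible.
- That value is used for the primary endpoint in place of LOCF.
- The reason for withdrawal and who initiated it are recorded.

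This changes data collection only. How to treat an NRS taken after a further index-knee procedure (item 2) is a separate question and is left as it is.

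The cost is protocol wording, one or two eCRF fields and a few calls. The downside is that a few scores would be taken by telephone rather than at the site.
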